11.4. Recording Adverse Events

Adverse events should be collected and recorded for each subject from the date the informed consent form (ICF) was signed until the end of their participation in the study, (i.e., the subject has discontinued or completed the study) through the follow-up visit with the exception of those subjects who discontinue study medication during the study and are followed on a semi-annual basis. Subjects who discontinue study medication but continue follow-up within the study will not have AEs collected after study drug discontinuation. Only those AEs that occurred while on study drug that have not been resolved will be followed until resolution or stabilization.

Following the end of the subject’s participation in the study, the CSSPI or an authorized delegate should report SAEs “spontaneously” if considered at least possibly related to study medication.

Adverse events may be volunteered spontaneously by the study subject, or discovered by the study staff during physical examinations or by asking an open, non-leading question such as, “How have you been feeling since you were last asked?” All AEs and any required remedial action will be recorded in the subject’s source documentation and transcribed onto the appropriate CRF page for the study period indicated. The nature of AE, date (and time, if known) of AE onset, date (and time, if known) of AE outcome to date, severity, and action taken of the AE will be documented together with the CSSPIs or an authorized physician’s assessment of the seriousness of the AE and causal relationship to study medication and/or study procedure (at the time of assessment).

All AEs should be recorded individually in the study subject’s own words (verbatim) unless, in the opinion of the PI or an authorized physician, the AEs constitute components of a recognized condition, disease, or syndrome. In the latter case, the condition, disease, or syndrome should be named rather than each individual symptom. The AEs will subsequently be coded using the MedDRA.

11.5. Treatment and Follow-Up of AEs

Appropriate measures should be taken to treat AEs as necessary, and the response of the study subject should be monitored and recorded. Clinical, laboratory, and diagnostic measures should be obtained as needed, and the results of which should be recorded in the subject's source documentation and transcribed onto the appropriate CRF page.

All SAEs will be followed until resolution, stabilization of the condition, the event is otherwise explained, or the subject is lost to follow-up.

11.6. Serious Adverse Events (SAEs)

An AE is considered serious if it meets one or more of the following criteria:

- Results in death
- Is life-threatening (i.e., a subject is at immediate risk of death at the time of the event, not an event where occurrence in a more severe form might have caused death)
- Requires inpatient hospitalization or prolongation of existing hospitalization
- Results in persistent or significant disability/incapacity
- Results in a congenital anomaly/birth defect
- Is another important medical event (see below)?

Important medical events that do not result in death, are not life-threatening, or do not require hospitalization may be considered SAEs when, based on appropriate medical judgment, they may jeopardize the subject and may require medical or surgical intervention to prevent one of the outcomes listed above. Examples of such medical events include allergic bronchospasm requiring intensive treatment in an emergency room or in a physician's office, blood dyscrasias or seizures that do not result in inpatient hospitalization, and the development of drug dependency or drug abuse. A distinction should be drawn between serious and severe AEs. Severity is a measure of intensity whereas seriousness is defined by the criteria above. For example, a mild degree of gastrointestinal bleeding requiring an overnight hospitalization for monitoring purposes would be considered an SAE, but is not necessarily severe. Similarly, an AE that is severe in intensity is not necessarily an SAE. For example, alopecia may be assessed as severe in intensity, but would probably not be considered an SAE.

11.6.1. SAE Reporting Requirements

The CSSPI or an authorized delegate is responsible for submitting the requested information via the DCC Online Adverse Event Reporting System within 24 hours or as soon as possible after learning of the event. Following the end of the subject's participation in the study, the CSSPI or an authorized delegate should report SAEs "spontaneously" if considered at least possibly related to study medication. Upon entry of a serious adverse event by a CSSPI, the DCC Online Adverse Event Reporting System will immediately notify the Medical Safety Monitor (MSM).

- Within **24 hours** (of learning of the event), investigators must report any Serious Adverse Events (SAEs). Investigators must report all other AEs within **5 working days/7 calendar days** (of learning of the event).

Serious adverse events: The CSSPI determines causality (related, probably related, possibly related, unlikely to be related, and unrelated) of the adverse event. The IMM will review the SAE report. The IMM may request further information if necessary. The Online Adverse Event Reporting System maintains audit trails and stores data (and data updated) and communication related to any adverse event in the study. The IMM may determine that the Serious Adverse Event requires expedited reporting to the Sponsor and FDA (Food and Drug Administration). The DCC will prepare a Medwatch safety report for submission to the FDA. If warranted, the IMM will notify the DSMB chair. The DSMB may suggest changes to the protocol or consent form to the Study Chair as a consequence of adverse events.

As a minimum requirement, the initial notification will provide the following information:

- Subject ID number
- Date of SAE onset
- An event term
- Details of SAE (if sufficient information is available)
- Criterion/criteria for classification as “serious”
- Causality assessment (if sufficient information is available to make this classification).

Initial reports of SAEs must be followed later with detailed descriptions, including clear photocopies of other documents as necessary (e.g., hospital reports, consultant reports, autopsy reports, etc.), with the study subject’s personal identifiers removed. All relevant information obtained by the CSSPI or an authorized delegate through review of these documents will be submitted on a follow-up SAE CRF page via the DCC Online Adverse Event Reporting System. The Independent Medical Monitor may also request additional information on the SAE.

Non-serious adverse events: Non-serious adverse events that are reported to or observed by the investigator or a member of his research team will be submitted to the DCC in a timely fashion (within 5 working days). The events will be presented in tabular form and given to the IMM on a quarterly basis or as requested. Local site investigators are also required to fulfill all reporting requirements of their local institutions.

The DCC will prepare aggregate reports of all adverse events (serious/not serious, expected/unexpected and relationship to study drug) for the IMM on a quarterly basis and the DSMB on a semi-annual basis, or as requested by either the IMM or DSMB. In addition, all adverse events will be coded using the MedDRA system. A separate report detailing protocol compliance will also be available from the DCC for DSMB review monthly or as requested.

Any AE fulfilling the criteria for expedited reporting will be reported by MediciNova and NeuroNEXT to regulatory authorities and Investigators, respectively, in accordance with the NeuroNEXT Network and company’s standard operating procedures (SOPs) and local regulatory requirements.

Clinical Study Site Principal Investigators are responsible for complying with NeuroNEXT Central Institutional Review Board’s (CIRB) reporting requirements for all safety reports.

Copies of each report and documentation of IRB notification and receipt will be kept in the investigator's study file. **Emergency Procedures**

If the CSSPI or an authorized delegate needs urgent advice regarding the management of an SAE or any other safety issue, an "on call" Independent Medical Safety Monitor(s) will be available 24 hours a day by telephone/pager. A neurologist experienced with MS trials and pharmacotherapy trial medical monitoring, independent of MediciNova or NINDS/NeuroNEXT or CCF, will be the primary medical safety monitor.

11.6.2. Emergency Treatment Code-Break

In the case of a medical emergency, where knowledge of study treatment by the CSSPI or an authorized delegate is essential for immediate medical management, the CSSPI or an authorized delegate should contact the study IMM to discuss the code break prior to revealing the treatment identity.

A 24-hour code-break service will be available via the DCC.

All treatment code breaks must be fully documented and signed with the time, date, reason, and name of person responsible for breaking the blind and tracked on the unblinding log. The breaking of the blind must result in the withdrawal of the subject, and the subject should return for a final study assessment.

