After Day 15, subjects with intolerable side-effects (eg nausea, diarrhea, vertigo) may reduce their dose to either 4 capsules twice a day (80 mg/d for those taking ibudilast) or 3 capsules twice a day (60mg/d for those taking ibudilast). Subjects with intolerable side-effects (eg nausea, diarrhea, vertigo) at the end of Day 14 may continue to taking 3 capsules twice a day at the Investigator's discretion. At the investigator's discretion, the daily dose of ibudilast can be changed between 3 capsules twice a day, 4 capsules twice a day, and 5 capsules twice a day over the first 8 weeks of treatment. At the end of the first 8 weeks of treatment, the subject must maintain their then-current daily dose of study medication (3 capsules twice per day, 4 capsules twice per day, or 5 capsules twice per day) for the duration of the trial. Additionally, at the investigator's discretion, the daily dose of ibudilast may be divided and taken three times per day to help improve tolerability.

Subjects will return to the clinic for follow-up visits on a regular basis at Weeks 4, 8, 12, 24, 36, 48, 60, 72, 84 and 96 (see Table 1 Schedule of Assessments).

Subjects who experience a relapse will return to the clinic within three days of notifying the Investigator and will undergo assessments described in Table 2 Schedule of Unplanned Procedures and Assessments).

Subjects who prematurely discontinue study medication will continue to be followed on a semi-annual basis (Table 2 Schedule of Unplanned Procedures and Assessments) until the end of the study (Week 96).

For subjects who are no longer taking study drug and are being followed on a semi-annual basis (Wk 24, 48, 72, 96), adverse events will not be collected post study drug discontinuation. Existing AEs will be followed until the AE resolves or stabilizes.

Follow-up Phase

All subjects who complete the study active on study medication will return for a follow-up safety visit at Week 100 (4 weeks after their last study visit) to assess general health and adverse event status.

Number of Subjects (Planned): The number of randomized subjects planned for this study is 250: 125 in the placebo treatment group and 125 in MN-166 100 mg/d treatment group.

Study Entry Criteria:

Inclusion Criteria:

- Written informed consent is obtained and willing and able to comply with the protocol in the opinion of the Investigator
- Male or female subjects ages 21 to 65, inclusive

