4. For subjects who prematurely discontinue study medication, a semi-annual (SA) visit will be conducted at Weeks 24, 48, 72, and 96

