Subjects who experience symptoms suggestive of a possible relapse will return to the clinic within three days of notifying the Investigator and will undergo assessments described in Table 2 Schedule of Unplanned Procedures and Assessments).

Subjects who prematurely discontinue study medication will be asked to continue to be followed off study medication on a semi-annual basis (Table 2: Schedule of Unplanned Procedures and

[figure not shown]
Assessments) until the end of the study (Week 96). See section 7.3.1 for addition details regarding drug discontinuation procedures.

Randomization will be performed at the double-blind baseline visit using an Interactive Voice/Web Response System (IXRS).

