7.3.1. Follow-up Procedures Upon Discontinuation/Withdrawal

If a subject discontinues study medication for any reason, the subject will be encouraged to continue to be followed within the study, but on a reduced study visit schedule. Depending upon when the subject discontinued study drug, the reduced study visit schedule will include study visits at Week 24, 48, 72, and 96. The timing of all study visits will remain relative to the original baseline date. For subjects who discontinue study drug between regularly scheduled study visits, the subject should complete the next regularly scheduled study visit after study drug discontinuation, and then shift to the reduced study visit schedule. For subjects who discontinue study drug at a regularly scheduled study visit, the subject should shift immediately to the reduced study visit schedule. For subjects discontinuing study drug but remaining in the study for follow-up, study visits will occur on an approximate semi-annual basis until Week 96. Table 2 outlines the procedures and assessments to be conducted in subjects remaining in the study for follow-up but are off study medication. After study drug discontinuation, new-onset AEs will not be collected.

If a subject discontinues/withdraws prior to study completion and does not wish to continue follow-up within the study (i.e. return for semi-annual visits), then all assessments scheduled for the Early Withdrawal visit (Table 2) should be performed at the time of study discontinuation.

A termination CRF page should be completed for every subject who received study medication whether or not the subject completed the study. The reason for discontinuation should be indicated on the CRF. Any AEs that are present at the time of discontinuation/ withdrawal should be followed in accordance with the safety requirements outlined in Section 11.

For all subjects who complete the study on study medication, a follow-up visit (Week 100) will be conducted 4 weeks after the last visit to assess general health and adverse event status.

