Between scheduled study visits, subjects with new or significant worsening MS symptoms that last 24 hours in duration and occur in the absence of fever or infection should notify the Investigator immediately and be seen for an Unscheduled Relapse Evaluation Visit within 3 days of notifying the Investigator. The following assessment should be performed at the Relapse Evaluation Visit:

- Body weight
- Vital signs
- Interval history
- Adverse event monitoring
- Concomitant medication review
- SF-36
- MSIS-29
- SBQ-R
- BPI
- EDSS by blinded neurologist

Subjects continuing follow-up off study medication do not need to return for Unscheduled Relapse Evaluation Visits. If during a regularly scheduled study visit, a relapse episode is noted, complete the relapse evaluation assessments above along with the scheduled assessments for that study visit.

Semi-Annual Visits (for subjects who discontinue study medication)

Subjects who discontinue study medication and remain in the study for follow-up will be followed on a semi-annual basis (Week 24, 48, 72, and 96, relative to Baseline). The following assessments will be performed at each semi-annual visit:

- Relapse assessment
- Cognitive tests (SDMT and SRT)
- BPI
- SF-36
- MSIS-29
- EQ-5D
- SBQ-R
- MSFC

- EDSS
- Brain MRI
- OCT

Early Withdrawal Visit

Subjects who discontinue study medication and choose not to be followed on a semi-annual basis will undergo the following assessments:

- Physical examination
- Body weight
- Vital signs
- Interval history
- Adverse event monitoring
- Concomitant medication review
- Cognitive tests (SDMT and SRT)
- BPI
- SF-36
- MSIS-29
- EQ-5D
- SBQ-R
- Hematology, chemistry, lipid profile, and urinalysis lab
- Serum biomarker samples
- ECG (12-lead)
- MSFC
- EDSS
- Brain MRI
- OCT
- Lumbar puncture (optional)
- Return of used/unused study drug bottles, study drug accountability and compliance check

Laboratory Re-test visit

Subjects who have a clinically significant abnormal lab finding may return for a laboratory re-test visit and will have the following assessments performed at the discretion of the CSSPI:

- Interval history
- Hematology, chemistry, or urinalysis lab, as indicated

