Subjects who prematurely discontinue study medication will continue to be followed on a semi-annual basis until the end of the study. For such subjects, adverse events will not be collected post study drug discontinuation. Existing AEs will be followed until the AE resolves or stabilizes.

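### Section 11.6.2 takes a subject out of the study when the blind is broken; ending study drug only, with off-drug MRI still offered to Week 96, would be a minor and cheap improvement

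*Combined protocol and SAP*

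**What the plan says.** Protocol 11.6.2 allows a code break only in a medical emergency, after discussion with the medical monitor. It then orders: "The breaking of the blind must result in the withdrawal of the subject", and adds that "the subject should return for a final study assessment".

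The general rules for stopping study drug point to continued follow-up:

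- Synopsis: "Subjects who prematurely discontinue study medication will continue to be followed on a semi-annual basis", to Week 96.
- Protocol 6.1.2: such subjects "will be asked to continue to be followed off study medication on a semi-annual basis".
- Protocol 7.3.1: "If a subject discontinues study medication for any reason, the subject will be encouraged to continue to be followed within the study".
- Protocol Table 2, note 4: "a semi-annual (SA) visit will be conducted at Weeks 24, 48, 72, and 96". The table marks brain MRI for these visits.
- Protocol 8.8.1, Semi-Annual Visits: "Subjects who discontinue study medication and remain in the study for follow-up will be followed on a semi-annual basis". The list there includes brain MRI.
- SAP section 1: "Subjects who prematurely discontinue study medication will continue to be followed on a semi-annual basis until the end of the study".

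None of these mentions code breaks. SAP 6.1.1 analyses mITT subjects in their randomized arm whether or not they kept taking study drug.

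**The concern.** Withdrawing the subject and holding one last assessment reads as leaving the study, not merely stopping drug. A subject who stops drug for any other reason is invited to have scans to Week 96; an unblinded subject is not. Protocol 8.8.1 reserves the Early Withdrawal visit for those who choose not to be followed, and 11.6.2 removes that choice.

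The as-randomized analysis can use scans taken off drug. Without them, the linear mixed model in effect carries the on-drug slope over time spent off drug.

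The usual reason for removing unblinded subjects is to protect outcomes that knowledge of treatment can influence. That reason is weak here. The primary and major secondary efficacy endpoints are all imaging. SAP 2.1 describes BPF as computed by an automated algorithm and processed centrally. Protocol 8.8.2.14.5 has EDSS done by a blinded neurologist. New adverse events are not collected off drug (7.3.1).

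There is a possible second effect before Week 24. SAP 6.1.1 spells out the required efficacy assessment as a Week 24, 48, 72 or 96 visit. Read literally, a dosed subject whose only later scan is an exit scan before Week 24 would leave the mITT set.

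**Working it through.** **Text.** Section 11.6.2 is compulsory. Sections 6.1.2 and 7.3.1 ask or encourage. The synopsis and SAP section 1 state continued follow-up as a fact. A subject in a code break loses every scan after the exit visit. If that visit is the Early Withdrawal visit, it includes one brain MRI (Table 2, 8.8.1).

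**Size.** There is no plan figure to reproduce. The documents give no code-break rate, and the pilot slopes and variances behind the power statement are not reported. What follows is an illustration.

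*From the documents:* scans at 0, 24, 48, 72 and 96 weeks; 125 per arm; 35% slowing; 10% dropout; alpha 0.10.

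*Assumed:*
- Exits are 1% per arm: 125 × 0.01 = 1.25 subjects. Sensitivity values are 0.5% and 2%.
- Placebo slope −1 and on-drug slope −0.65 per 48 weeks.
- Off-drug slope in the drug arm −(1 − 0.35p), where p is the share of benefit that persists.
- Other dropout is split evenly after Weeks 24, 48 and 72.
- Intercept variance is 20–400 times the residual variance, and slope variance (per 48 weeks squared) 0.1–2 times.

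*Hand check, no other dropout, p = 0.* With time t = 0, 1, 2, 3, 4 in 24-week units and exit at x, a followed subject's fitted slope moves from the on-drug to the placebo rate by the fraction

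w = Σ(t − 2)·max(t − x, 0) / 10.

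- Week 12 (x = 0.5): w = (−0.5 + 0 + 2.5 + 7)/10 = 0.9
- Week 24 (x = 1): w = (0 + 2 + 6)/10 = 0.8
- Week 48 (x = 2): w = (1 + 4)/10 = 0.5
- Week 72 (x = 3): w = 2/10 = 0.2

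Shift in slowing = 0.01 × 35 × w = 0.315, 0.28, 0.175 and 0.07 points. The generalized least squares expectation for the random intercept and slope model with a common baseline gives 0.28, 0.17 and 0.07 for Weeks 24, 48 and 72.

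*With the 10% other dropout,* subjects with complete scans weigh slightly more. The largest shift over the variance range, in percentage points, is:

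| Exits per arm | Benefit persisting | Wk 12 | Wk 24 | Wk 48 | Wk 72 |
|---|---|---|---|---|---|
| 0.5% | none | 0.17 | 0.15 | 0.09 | 0.04 |
| 1% | none | 0.34 | 0.30 | 0.19 | 0.08 |
| 1% | half | 0.17 | 0.15 | 0.09 | 0.04 |
| 2% | none | 0.68 | 0.60 | 0.38 | 0.15 |
| any | all | 0 | 0 | 0 | 0 |

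The shift is the estimate from scans up to exit (35.00 in every case) minus the estimate with every later scheduled scan taken. The Week 12 column compares with scheduled scans only. If the Week 12 exit scan is also kept in the followed-up data, a rerun gives 0.40 instead of 0.34 at 1%.

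**Power.** The anchor is an assumption: 80% power for 125/1.10 = 113.6 complete subjects per arm. With the 10% dropout and 1% exits, power is 80.4–81.7% on scans up to exit and 80.1–81.8% with full follow-up. Follow-up adds information, but where benefit fades it also dilutes the contrast, so the net change can go either way. With the effect held fixed, cutting off one subject per arm after Week 24 or 48 takes 80% to 79.7–79.8%.

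**mITT set.** Only SAP 6.1.1 has the week list. The synopsis, protocol 12.1.1 and SAP 7.1 ask for at least one efficacy assessment in the double-blind phase and name no weeks, so an exit MRI could qualify. SAP 7.1 moves an off-schedule visit to the next scheduled one only for the categorical-time model.

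**The case against.** **A specific rule may override a general one.** Section 11.6.2 deals with unblinded subjects, and the other sections deal with stopping drug. A reader might infer a flat contradiction that a site cannot obey. The texts can be read as rule and exception, so that goes too far. What stands is that the exception is compulsory, is not acknowledged in the SAP, and serves little purpose for imaging.

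**There is a reason for withdrawal.** MSFC, MSIS-29, SF-36, EQ-5D and BPI are listed secondary outcomes and can be affected by knowing the arm. SAP 8.5 leaves them out of the final study report, but they are still planned. This supports flagging such data; it does not support stopping MRI. BPF results are visually verified at the analysis centre, so that centre must stay blinded.

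**The shift is not plainly a bias.** In the illustration, scans up to exit return the true on-drug slowing. They overstate only against an as-randomized target that includes time off drug. SAP 6.1.1 supports that target, but no formal estimand is stated. The same points are a correction for one target and dilution for the other. This stands.

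**Full follow-up is a best case.** Section 7.3.1 only encourages it, and these subjects have just had a medical emergency. This stands, and makes the achievable change smaller than the table's upper values.

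**Informative missingness.** Because a code break follows an emergency, a reader might infer that the loss is non-ignorable and biases the primary result. That would require exit to depend on the unseen BPF course, given the scans already taken. The documents do not show this, and the calculation models only a slope change after stopping drug.

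**Wider study exit.** A reader might also infer that protocol 7.3 and 8.4 push many more subjects out of the study for adverse events, laboratory values or non-compliance. Both sections are permissive; 8.6.2 continues assessments while drug is withheld, and 8.6.3 ends drug only. They do not enlarge the effect of 11.6.2.

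**Conclusion.** The point holds as a minor, cheap improvement. Section 11.6.2 compels study exit where the rest of the plan offers off-drug MRI to Week 96, and the blind-protection reason for ending MRI is weak.

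The expected effect on the primary result is very small: 0 to about 0.34 points of a 35% slowing at an assumed 1% exit rate, and zero if benefit persists off drug. No power gain should be claimed. This rests on an assumed code-break rate, assumed variances and full attendance after exit.

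Loss from the mITT set before Week 24 is possible only on a literal reading of SAP 6.1.1. The case for acting is that the change costs little and scans not taken cannot be recovered, not that the primary conclusion is at risk.

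**What to change.** Reword 11.6.2 so that breaking the blind *must result in discontinuation of study drug; the subject is encouraged to continue on the off-drug schedule in 7.3.1, at minimum brain MRI, unless consent is withdrawn or MRI is clinically inappropriate*. In addition:

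- Keep the EDSS rater and the MRI reading and analysis centres blinded after a site code break.
- Flag self-reported outcomes collected after unblinding, so that a sensitivity analysis can leave them out.
- Optionally, align the permissive wording in 7.3 and 8.4 with 7.3.1.

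The rules on when drug must stop do not change.

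The cost is protocol wording and a few extra scans at visits Table 2 already provides. Off-drug time dilutes the estimate slightly, by the same 0 to about 0.34 points at 1% exits. Some flagged self-report data will come from subjects who may know their arm.
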